6.3.2 Selection of Principal Investigators

Principal Investigators will require relevant research experience and commitment during early stage feasibility assessment. All investigators will have the particular medical expertise necessary to conduct the study in accordance to the protocol and all regulatory and ethical requirements. Written agreement to conduct

IRAS ID: 293186 Page **23** of **63**

research as such will be obtained prior to site initiation. A suitable co-investigator should be identified at each site to deputise in case of PI absence.

6.3.3 Pilot study

During the six months internal pilot we aim to recruit 20% of the total participant number (153) and this will be the primary target.

We will employ the following additional traffic-light criteria with regards proceeding to the full trial (Table 2):

- RED: Average recruitment rate falls below 1.275 patients per site per month, or the number of sites opened is less than 10, or the number of participants who have received the intervention they were randomised to is below 80% unless there are mitigating circumstances, determine that recruitment is not feasible and decide not to proceed;
- AMBER: Average recruitment rate per site per month is between 1.275 and 2.55*, or the number of sites opened is between 10 and 15, or the number of participants who have received the intervention they were randomised to is between 80% and 99% review recruitment strategies, report to TSC and NIHR HTA and continue with a modified recruitment strategy.
- GREEN: The primary target for this metric will be recruiting 153 patients. Other metrics will include average recruitment rate per site per month exceeding 2.55* (100% target rate) and 16 or more sites opened and the number of participants who have received the intervention they were randomised to is equal to 100%—proceed with trial.

Following the pilot phase, the main phase will be completed within 12 months. In addition, the IDSMC will monitor and report on all aspects of trial performance during the pilot phase, most notably compliance to trial intervention and secure recording of the primary outcome measure.

Table 2; Revised internal pilot grade scoring system

	Red	Amber	Green
Average recruitment rate (patient/centre/month)	<1.1.275	1.275- 2.55*	>2.55*
Number of sites open	<10	10-15	>15
Percentage of those randomised that agree to comply with the allocated intervention	<80%	80-99%	100%

^{*153/60 (}number of patients recruited/number of recruitment months across open sites).

IRAS ID: 293186 Page **24** of **63**

7 ELIGIBILITY CRITERIA

The CF STORM trial aims to recruit a minimum of 572 patients based on revised sample size calculations described in Section 13.1.1. All participants and participant's Legal Representative if applicable must provide written, informed consent / assent before any study procedures occur (see Section 10.2 for more information regarding informed consent processes) and must meet all eligibility criteria as described below.

7.1 Inclusion Criteria

Patients eligible for the trial must comply with all of the following at randomisation:

- 1. Clear diagnosis and clinical features of CF.
- 2. One or two Phe508del variants.
- 3. Established on daily mucoactive nebulised therapy (hypertonic saline or dornase alfa or both) for at least 3 months.
- 4. 6 years-of-age or older.
- 5. Established on Kaftrio[™] for at least 3 months.
- 6. Enrolled on the UK CF Registry.
- 7. Able to undertake spirometry.
- 8. No need for extra antibiotics (oral or intravenous) in previous two weeks.
- Completed informed consent and assent if applicable obtained from the participant, participant 's
 parent or legal representative and agreement of participant to comply with the requirements of the
 study

7.2 Exclusion Criteria

Any patient meeting any of the criteria listed below at baseline will be excluded from study participation:

- 1. Significant adverse reaction to Kaftrio™ requiring dose change during the 3 months prior to screening.
- 2. ppFEV₁ below 40% after Kaftrio™ therapy at any point during the 3 months prior to screening.
- 3. History of solid organ transplant or placed on active transplant waiting list.
- 4. Other non-CF condition that, in the opinion of the local CF team, significantly impacts on clinical progress.
- 5. Participation in a CTIMP within the last 3 months (the 3-month period does not apply to open label Kaftrio™ CTIMPs).
- 6. Prescribed Mannitol dry powder for inhalation as part of usual daily CF care within the last 6 weeks.

7.3 Co-enrolment Guidelines

Co-enrolment in another interventional CTIMP is not considered acceptable because it will introduce biases and negatively impact trial integrity. Only co-enrolment to a non-CTIMP trial is acceptable.

IRAS ID: 293186 Page **25** of **63**

8 TRIAL TREATMENT/INTERVENTIONS

8.1 Introduction

Eligible patients will be randomised to either 'STOP' or 'CONTINUE' daily nebulised mucoactive therapies. Patients in the 'CONTINUE' arm of the trial will continue to receive daily dornase alfa, hypertonic saline or both (as per the guidance of their local CF team) and patients in the 'STOP' arm will no longer receive daily dornase alfa, hypertonic saline or both.

8.2 Treatment Name / Description

8.2.1 'CONTINUE' arm - Dornase alfa

Active ingredient: Dornase alfa
Formulation: Nebuliser solution
Manufacturer: Local pharmacy stock

Packaging, storage and stability: Refer to SPC

Supplier's name: Local pharmacy stock Regulatory Status: Market Authorised

8.2.2 'CONTINUE' arm - Hypertonic saline

Active ingredient: Hypertonic saline
Formulation: Nebuliser solution
Manufacturer: Local pharmacy stock

Packaging, storage and stability: Refer to Patient Information Leaflet (PIL)

Supplier's name: Local pharmacy stock

Regulatory Status: CE Device

8.3 Manufacturing and Distribution

Intervention supplies are sourced from usual NHS stock.

8.4 Preparation, Dosage and Administration

8.4.1 Dornase alfa

One ampoule (2.5mg) of Dornase alfa should be inhaled using a nebuliser once or twice per day. Sites should refer to the current SPC, which can be accessed via https://www.medicines.org.uk/emc/, for all treatment decisions.

8.4.2 Hypertonic saline

One ampoule (4ml (3-7%) sodium chloride solution) of hypertonic saline should be inhaled using a nebuliser two to three times per day. Sites should refer to the current PIL for all treatment decisions.

8.5 Treatment Modifications

After the patient has entered the trial, the clinician is free to consider alternative treatment to that specified in the protocol, at any stage, if s/he feels it to be in the best interest of the patient. However, the reason for

IRAS ID: 293186 Page **26** of **63**

doing so should be recorded in the CF STORM Module and the patient will remain within the trial for the purpose of follow-up and data analysis according to the treatment option to which they have been allocated. Similarly, the participant/Legal Representative remains free to withdraw at any time from the protocol treatment and trial follow-up without giving reasons and without prejudicing further treatment.

8.6 Assessment of Compliance to trial allocation

CF STORM is an open label pragmatic trial and compliance to the trial intervention is a key factor when considering the non-inferiority design. We have established a four-point plan to support and monitor compliance with the trial intervention. This will be evaluated by the IDSMC in the pilot phase of the trial.

The four distinct processes to support and monitor compliance with the trial allocation;

- When introduced to the trial, patients will be able to access the trial website, which will include the ethics-approved patient information sheets and videos explaining the trial, in particular the importance of adhering to treatment allocation. Prior to recruitment physicians will be trained to ensure that patients are fully informed and willing to enter into the study and to comply with either the 'STOP' or 'CONTINUE' allocation.
- At each encounter, investigators will be trained to discuss compliance with the allocation with the patient. This will be recorded in the CF STORM trial module.
- In addition, patients will receive an automated email every three months. This will thank them for their support for the trial and include a short survey to assess their compliance with trial allocation, to ask them if they are happy to continue and whether they have complied with their allocation. The data from this survey will be stored on the CF STORM study module.
- More detailed objective monitoring of adherence data will be collected throughout the study. These data will be recorded from patients who have the capacity to provide electronic data capture from their nebuliser device and do this as part of their standard clinical care. For these patients, we will record data 3 months prior to randomisation, baseline data, encounter data and trial-end data. For patients in the pilot phase, we will collect baseline data and at the three-month time point. The adherence to nebulised therapies will be calculated as the proportion of taken doses compared to the expected number of doses agreed with and prescribed by the CF team (unadjusted adherence). These data will be reviewed by the IDSMC and inform the evaluation of the pilot phase. To optimise data collection, we will be opening pilot sites that regularly undertake electronic data capture as part of clinical practice, however patients not routinely collecting these data will not be excluded from the pilot as this would disadvantage patients with less severe lung condition, who may only be taking dornase alfa (and therefore not using a device that enables data capture).

8.7 Concomitant Medications/Treatments and Specific Restrictions

8.7.1 Medications Permitted

Refer to SPC / PIL guidance.

The COVID-19 vaccination can be administered where appropriate without any consideration for timing etc. in relation to the trial intervention.

8.7.2 Medications Not Permitted/ Precautions Required

Refer to SPC / PIL guidance.

IRAS ID: 293186 Page **27** of **63**

8.7.3 Data on Concomitant Medication

The name and duration of all chronic concomitant medications and additional antibiotics will be documented in the UK CF Registry / CF STORM Module. The dosage will also be recorded for dornase alfa and hypertonic saline. The researcher should reassess all concomitant medications at each encounter with the participant. Any medications introduced/discontinued should be documented.

8.8 **Overdose**

The occurrence of an overdose which has resulted in an AR should be reported via the complication tab on the UK CF Registry. The effect of dornase alfa overdose has not been established. Systemic toxicity of dornase alfa has not been observed and is not expected due to the poor absorption and short serum half-life. Systemic treatment of overdose is therefore unlikely to be necessary. Overdose of hypertonic saline through substantial oral ingestion may require the use of a diuretic to remove excess sodium.

Specific information on reporting adverse events can be found in Section 11.

IRAS ID: 293186 Page **28** of **63**

9 **OUTCOMES**

9.1 **Primary Outcome**

The primary outcome is the change in percent predicted Forced Expiratory Volume in One Second (ppFEV₁) measured in a clinical encounter at baseline and trial-end at 52 weeks.

Respiratory function, as determined by spirometry, is a key outcome for pwCF in determining the efficacy or safety of an intervention.

In response to the COVID-19 pandemic, funding has been secured to provide pwCF with devices that enable home spirometry. These have been rolled out successfully in the UK and have facilitated home monitoring of pwCF during this period. Centres have provided patients with clear guidance on how to perform spirometry and the newer devices enable central monitoring of quality.

Studies suggest that home spirometry results in consistent values over time in an individual. To avoid any systematic bias between home and hospital spirometry values, baseline and trial-end spirometry measurements must be undertaken on the same device in the same location.

The preferred option for collecting the primary outcome is for ppFEV₁ to be measured by spirometry performed in hospital, however if this is not possible then the home spirometry should be undertaken using an established standard operating procedure for the clinic and with central monitoring by the CF team and/or respiratory physiologist of the quality of the technique (see researcher manual for further guidance).

For patients undertaking home spirometry, at baseline participants will be asked to collect three measures at least one day apart before starting the intervention (over a maximum period of 5 days). Similarly, three home spirometry measures will also be requested for the final study visit (again over a maximum period of 5 days which incorporates the final visit date) prior to reverting to standard care. Each should be recorded on the registry.

To ensure uniform calculation of ppFEV₁ across all trial sites, the raw spirometry values for FEV₁ (ml) will be recorded on the UK CF Registry and these will be converted to ppFEV₁ through an internationally accepted formula embedded in the UK CF Registry database. (10) This will require a reliable height measurement and for patients who are still growing, a stadiometer will be used for accurate height measurement at home.

Baseline $ppFEV_1$ should be recorded on the day of randomisation (no earlier than 14 days before randomisation). The trial-end $ppFEV_1$ should be recorded at the final trial visit at 52 weeks (time point 1; range 51-55 weeks).

IRAS ID: 293186 Page **29** of **63**

9.2 **Secondary Outcome(s)**

Objectives	Outcome Measures	Timepoint(s) of evaluation		
Efficacy:				
To assess longitudinal patterns of change in ppFEV ₁ over the trial period	ppFEV₁	Time points 0 and 1, and any time points between (encounters during trial period)		
To assess change in respiratory function between baseline and 52 weeks	Percent predicted Forced Vital Capacity (ppFVC)	Time points 0 and 1		
To assess change in respiratory function over the trial period	Forced Expiratory Flow between 25-75% of vital capacity (ppFEF ₂₅₋₇₅)	Time points 0 and 1		
To determine the need for extra antibiotic treatment	Number of courses and total number of days of extra antibiotics (oral, intravenous and nebulised)	Time points 0 and 1		
To determine the need for extra chronic medications	Number of courses and total number of days of chronic medications (oral and nebulised)	Time points 0 and 1		
To determine the number and proportion of respiratory cultures positive for significant pathogens	Positive respiratory culture for new significant pathogens	Time points 0 and 1, and any encounters between		
To determine need for hospital admissions	Number of separate hospital inpatient stays. In addition, total number of inpatient days (subdivided into total IV days and total non-IV days)	Time point 1 and any encounters between		

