10.7 Schedule for Assessments and Follow-up

All assessments at baseline and study completion are to be conducted in line with the Schedule of Assessments below. All follow up encounters until 52 weeks will be conducted in line with standard consultations.

Schedule of Assessments:

Procedures/ Assessments	Screening	Baseline/ Randomisation (Time Point:0 (0 weeks) *	12 weeks	17 weeks	26 weeks	34 weeks	39 weeks	50 weeks	Any interim encounters (Time Point 0-	Study Completion (Time Point:1 (52 weeks (- 1/+3 weeks))	Premature Discontinuation
Signed e-Consent/ e- Assent Form		Х									
Assessment and confirmation of Eligibility Criteria	Х	Х									
Review of Medical History	Х	Х									
Review of any clinician defined pulmonary exacerbation									Х	Х	X
Review of Concomitant Medications	X	X							Х	Х	X
Randomisation		Х									
Study Intervention**		Х	Х	Χ	Χ	Χ	Χ	Χ	Х	Х	
3-month pre- randomisation data collection of nebuliser data from electronic devices		(X)									
Compliance with trial allocation		X							Х	Х	Χ
Survey of trial progress (email)			Х		Х		X				
Objective adherence to nebulised therapies (if collected routinely)									(X)	(X)	(X)
Height and weight		Χ							(X)	X	X
Assessment of Adverse Events		X							(X)	Х	Х
Spirometry	Χ	Х							(X)	Х	(X)
Respiratory cultures		(X)							(X)	(X)	(X)
Hospital inpatient stays									(X)	Х	(X)

IRAS ID: 293186 Page **34** of **63**

Procedures/ Assessments	Screening	Baseline/ Randomisation (Time Point:0 (0 weeks) *	12 weeks	17 weeks	26 weeks	34 weeks	39 weeks	50 weeks	Any interim encounters (Time Point 0-	Study Completion (Time Point:1 (52 weeks (-	Premature Discontinuation
Pregnancy assessment		(X)							(X)	(X)	(X)
EQ-5D-5L generic QoL measure (email)		Х		Х		Х		Χ			(X)
CFQ-R disease specific QoL measure		Х						Χ	(X)		(X)
Airway clearance techniques recorded on the UK CF Registry		Х								Х	-

⁽X) – As indicated/appropriate.

Baseline / Randomisation Visit (0 Weeks)

The following data should be collected and assessments/activities performed:

- Assessment of Eligibility Criteria
- · Signed Consent Form (& Assent Form for minors)
- Review of Concomitant Medications (will determine number of courses and total number of days of extra antibiotics and chronic medications)
- · Study allocation recorded in patient notes
- Review of medical history
- Height and weight
- Spirometry for assessment of percent predicted Forced Expiratory Volume in 1 second (ppFEV₁)

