10.8.1 Premature Discontinuation of Trial Intervention

Participants may not comply with the trial allocation for reasons including, but not limited to:

- Participant-led, i.e. request by the participant / Legal Representative
- Unacceptable toxicity (see Section 11 for Adverse Event reporting)
- Intercurrent illness preventing further treatment of allocated intervention
- Death
- Clinician-led:
 - Any change in the participant's condition that justifies the discontinuation of the treatment allocation in the clinician's opinion.
 - Reasons of non-adherence or non-compliance with treatment allocation or other trial procedures.
 - Participant meets an exclusion criterion (either newly developed or not previously recognised). This includes discontinuation of Kaftrio[™], but not a reduction in FEV₁ below 40%. If there is a transient fall in FEV₁ below 40% this should be managed as appropriate by the local team.
 - Participant unable to follow allocated treatment arm for 4 weeks.

Discontinuation from study intervention does not mean discontinuation of the study altogether, and the remaining follow up assessment and data collection should be completed as indicated in the protocol (unless consent is specifically withdrawn, see section 10.8). Every follow-up encounter at and after the participant's premature discontinuation of trial intervention should record that the participant is no longer on the allocated treatment arm.

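### The secondary outcome on extra chronic medications counts only oral and nebulised drugs, so a chronic inhaled dry powder started on trial, such as mannitol, is recorded but not counted

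*Protocol*

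**What the plan says.** In the section 9.2 table, the objective on extra chronic medications carries no route limit, and neither does the matching line in the Protocol Overview (section 3). The measure does: "Number of courses and total number of days of chronic medications (oral and nebulised"). The row above it, on extra antibiotics, has its own and different list: oral, intravenous and nebulised.

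Recording is broader than counting. Section 8.7.3 says: "The name and duration of all chronic concomitant medications and additional antibiotics will be documented". It also asks for any medication introduced or discontinued to be documented. The visit lists in section 10.7 contain the line "Review of Concomitant Medications (will determine number of courses and total number of days of extra antibiotics and chronic medications"), with no route for either group.

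On dry powder, exclusion criterion 6 in section 7.2 reads: "Prescribed Mannitol dry powder for inhalation as part of usual daily CF care within the last 6 weeks". By contrast, dornase alfa "should be inhaled using a nebuliser once or twice per day" (section 8.4.1), and section 8.4.2 describes hypertonic saline in the same way.

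On treatment after entry, section 8.7.2 says only "Refer to SPC / PIL guidance". Section 8.5 leaves the clinician free to use alternative treatment at any stage, with the reason recorded and the participant kept in follow-up and analysis. Section 10.8.1 lists, among clinician-led reasons for leaving the allocation, "Participant meets an exclusion criterion (either newly developed or not previously recognised"), but adds that "Discontinuation from study intervention does not mean discontinuation of the study altogether".

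**The concern.** The outcome is there to show whether people who stop nebulised mucoactive drugs, or who stay on them, need other long-term treatment added. An inhaled dry powder is a plausible addition in a trial about withdrawing inhaled mucoactive drugs, and mannitol is the one such product that the protocol singles out at entry. The bracket in section 9.2 leaves that route out. An analyst who follows section 9.2 literally would record no added chronic treatment for a participant who took a dry powder for most of the year, although the entry is in the trial data. The outcome would then understate what its own objective asks for.

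**Working it through.** The plan states no figure on this point, so the check is mainly textual. A short calculation then bounds the possible size.

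**Step 1: is dry powder within the bracket?** The two routes in section 9.2 are oral and nebulised. Section 7.2 names mannitol as a powder for inhalation. Sections 8.4.1 and 8.4.2 describe the trial drugs as taken through a nebuliser. In the protocol's own terms a dry powder is inhaled, but it is neither oral nor nebulised. The different list in the antibiotic row suggests that the brackets are meant as route lists.

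**Step 2: can it arise on trial?** Exclusion 6 looks back 6 weeks from entry. Section 8.7.2 names no banned drug, and section 8.5 permits alternative treatment. Starting mannitol may count as newly meeting an exclusion criterion under section 10.8.1. That is a reason to leave the allocation, not follow-up, so the outcome is still computed for that participant.

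**Step 3: is it recorded?** Yes, under section 8.7.3, by name and duration.

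**Step 4: possible size.** The inputs are 52 weeks of follow-up, with completion at weeks 51 to 55 (sections 9.1 and 10.7), and 286 randomised per arm (section 13.1.2).

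- Counted under section 9.2 as written: 0 courses and 0 days.
- Upper bound for one participant with continuous use: 1 course and 52 × 7 = 364 days. Over the completion window this is 51 × 7 = 357 to 55 × 7 = 385 days.
- Shift in the arm's mean days per such participant: 182 / 286 = 0.64 days for 26 weeks of use, and 364 / 286 = 1.27 days for 52 weeks.
- If a share p of an arm used a dry powder for 26 weeks, the mean is understated by p × 182 days. This gives 0.01 × 182 = 1.8, 0.02 × 182 = 3.6 and 0.05 × 182 = 9.1 days.

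The shares of 1%, 2% and 5% are assumptions. The protocol gives no frequency of on-trial mannitol use, and at p = 0 the shift is zero.

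**The case against.** The strongest reply is that an operational measure may be narrower than its objective, and that a registry trial may record more than any one outcome counts. This is right as far as it goes. Broad recording has its own purpose, because the economic evaluation in section 13.4.1 draws resource use from the registry. A reader might infer that section 9.2 contradicts sections 8.7.3 and 10.7, but the documents do not support that. Section 8.7.3 is a recording rule. The line in section 10.7 is visit-list shorthand: it omits the routes for antibiotics too, although section 9.2 gives them, so it does not redefine either outcome.

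A second reply is that *nebulised* may stand loosely for *inhaled*, since the Protocol Overview gives the route of the trial drugs as inhalation with nebulised in brackets. Section 9.2 does not say so, and the loose reading sits poorly with the separate wording used for mannitol in section 7.2. It cannot be ruled out, and clearer wording would settle it.

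A third reply is that mannitol use would not go unseen, because it would be documented as an introduced medication. This also stands. What is lost is its place in this count.

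A reader might also infer that the undercount favours STOP, on the view that a replacement drug would be started more often there. The documents give no usage data by arm, so neither a difference nor its direction is shown.

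**Conclusion.** The concern holds as a mismatch between one secondary objective and its measure. The objective asks about any extra chronic medication, and the bracket in section 9.2 leaves out a route that is relevant to a trial of stopping inhaled mucoactive drugs. The protocol itself fixes the routes, so this is a stated rule that can undercount and not a detail left to the statistical analysis plan.

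The weight is minor. The conclusion rests on reading *nebulised* in its ordinary sense and on mannitol being possible after entry, which the protocol does not expressly prohibit. The actual size is unknown and may be zero. The primary ppFEV1 analysis, the sample size and the planned adjustment for treatment crossovers are unaffected.

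**What to change.** In section 9.2, change the routes for chronic medications from oral and nebulised to oral, nebulised and other inhaled, including dry powder. The reason is the objective itself. The change is not meant to make section 9.2 match sections 8.7.3 or 10.7, which have no route limit and would still be broader. In the report, add one descriptive line giving newly started mannitol by arm.

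The cost is one bracket and one line. Section 8.7.3 already collects the name and duration of every chronic medication, so no new data, visits or participants are needed. The change is best made before any comparative analysis. The arm definitions, section 10.8.1, the intention-to-treat analysis and the crossover methods stay as they are.
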